4.6.3. Safety summary of Phase 2 MS trial (MN-166-CL-001)

In a Phase 2 trial conducted in CEE in RRMS patients, subjects were treated with either placebo or MN-166, 30 or 60 mg/d up to two years. Enrolled subjects received study drug for 12 months in the “core period” and if eligible, continued to the “extension period” for an additional 12 months of treatment. A total of 297 subjects were enrolled, 103 subjects were randomized to placebo group, 95 subjects were randomized to the 30 mg/d group and 99 subjects were randomized to the 60 mg/d group. Two-year completion of the 60 mg/d group was 86%.

Core period (12 m) 1 st year	# of enrolled subject	Extension period (12 mo) 2 nd year	# of enrolled subjects

CONFIDENTIAL

	(N)		(N)
Placebo	103	P-30mg	49
		P-60mg	48

During the 12-month double-blind core-period, the adverse events most frequently reported (> 5%) occurred in the SOCs of Infections and Infestations (36%), Nervous System Disorders (19%), Gastrointestinal Disorders (15%), Psychiatric Disorders (13%), General Disorders and Administration Site Conditions (9%), and Musculoskeletal and Connective Tissue Disorders (7%). No significant differences in TEAEs by SOC were observed between treatment groups. There was a slight dose related increase in the percent of subjects with gastrointestinal AEs: 8%, 12%, and 15% for placebo, 30 mg/d, and 60 mg/d treatment groups, respectively.

During the core-period, more treatment-related TEAEs were experienced by subjects in the 60 mg/d group (26 TEAEs) compared to the 30 mg/d (18 TEAEs) or placebo group (12 TEAEs). The most common treatment-related AEs were headache (n =3) and nausea (n =2) in the 30 mg/d; nausea (n =4), headache (n =3), vomiting (n=2) and dizziness (n =2) in the 60 mg/d group; and upper respiratory infection (n =5) and headache (n =2) in the placebo group.

During the 12-month open-label extension period, five additional treatment-related TEAEs occurred. These TEAEs were night cramps (1 subject 60 mg/d), hepatotoxicity (1 subject 60 mg/d), depression (1 subject 60 mg/d), and pruritus (2 subjects in placebo to 60 mg/d).

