6. ANALYSIS POPULATIONS

Due to the exploratory nature of this study, all analyses to address the primary and major secondary objectives will be conducted at the 0.10 significance level. The analysis population of interest will differ depending on the objectives of any particular analysis.

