The analysis used the proposed time points of 0, 24, 48, 72, and 96 weeks. Power curves were computed for DS1, DS2, and for their average (Avg). Avg was based on averaging the LMM parameter estimates across the data sets (e.g., average slope = [DS1 slope + DS2 slope] / 2). Avg was an attempt to pool information from the two data sets without the raw data (the raw data for DS2 was unavailable). A 10% dropout rate was assumed and all estimated sample sizes were inflated by this percentage (i.e., final sample size = initial sample size \times 1.10). Given the resources required for obtaining and analyzing 3T scans, the type I error rate was set at $\alpha = 0.10$. Figure 7.1 shows power curves for the three smallest effect sizes (30%, 35%, and 40%). Focusing on Avg for the middle effect size (35%), the figure indicates that a single-arm $N / 2 = 125$ provides close to 80% (power = 0.80 is the horizontal dashed line). The middle effect size is important as it nearly corresponds to the upper effect size of the aforementioned Ibudilast study (effect size = 36%). The Avg data source is preferred because it approximates a pooling of the information from both samples. The feasibility of $N / 2 = 125$ as the single-arm sample size was examined by calculating power for effect sizes with $\alpha = 0.10$ for all three data sources (DS1, DS2, Avg). The power by effect size curve and data source is shown in Figure 7.2. The figure clearly shows that the study has adequate power across the range of possible values suggested by these two data sources. For the “best” data (DS1), our study has slightly less than 90% power to detect effects of approximately 40% or larger, and more than 90% power to detect effects on the upper end of the range of interest (50%). Most importantly, the figure shows that the power based on the Avg data source is very high for effects in the 33% - 36% range of greatest interest (approximately 80% - 85%). Therefore, based on these assumptions, we are confident that a per-arm sample size of $N / 2 = 125$ ($N = 250$ total participants) is sufficient to help ensure statistically reliable results for the proposed study.

Figure 9.1: Power as a Function of Single-arm sample size, effect size, and data set

[figure not shown]
[figure not shown]

Figure 9.2: Power as a Function of Effect Size and data source for sample size of 125 and alpha = 0.10

9.2. Primary Objective #2: Evaluate the safety and tolerability of Ibudilast (MN-166) versus placebo

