Pilot data was not available for the MTR power estimates. Descriptive statistics were provided by [name] (Director of NeuroRx) for a study of the efficacy of BG-12 (BG00012, dimethyl fumarate), which is a novel therapy in the development for relapsing MS. Ibudilast is purported to have neuroprotective effects, and so these data were used as a model to project the power of Ibudilast in this proposed trial. A total of $N = 448$ MS patients had whole-brain MTR measured at baseline, 24 weeks, 1 year, and 2 years as part of a multi-center phase III clinical trial using 1.5T MRIs and the stock manufacturer pulse sequence. Only descriptive statistics were available for change between baseline and two years. There was a placebo group and two treatment groups, one receiving BG-12 240 mg twice a day (b.i.d.) and the second receiving BG-12 240 mg three times per day (t.i.d.). The statistics available for the study were means of change scores and their standard deviations. Thus, power was estimated based on an independent t -test of the mean baseline to 2 year difference in MTR scores for the treatment (BG-12) and placebo groups. Power was computed using the conventional formula

$$1 - \beta = \Phi\left(\frac{|\delta|\sqrt{125}}{\sigma} - Z_{1-\frac{\alpha}{2}}\right)$$

where δ is the difference of the mean change scores and σ^2 is the pooled variance of the difference. A subset of patients had no new or enlarging T2 lesions, and the analysis was performed twice: once for all the patients and another time excluding the patients with no lesions. The results of the power analysis are shown in the table below. As seen in the table, the lowest estimated power (t.i.d., all patients) was greater than the conventional cut-off of 0.80. When only subjects with no new lesions were considered (which more closely approximates what we expect in the proposed trial), estimated power was even greater than the conventional level. The table suggests that $N = 250$ might provide sufficient power to detect T and P differences in change over time for the proposed study. The improved image acquisition from 3T MRIs and tailored pulse sequences are expected to increase the study power.

Table 9.1. Power as a Function of Treatment and Type of Patient for MTR

Treatment	Patients	Power
b.i.d.	All	0.856
t.i.d.	All	0.803
b.i.d.	No Lesions	0.925
t.i.d.	No Lesions	0.816

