The three levels of nesting represented by Equation (4) (month nested within eye nested within patient) presents a challenge for deriving power equations, and analytic results are usually based on simplifying assumptions (e.g., fewer random effects than in Equation (4)) (Heo and Leon, 2009). In order to base the power estimate on the LMM of Equation (4), a simulation approach was used. For the simulation, the LMM of Equation (4) was fit to the pilot data and then the resulting estimates were treated as parameters in the following replications. For each replication, a random number generator was used to compute random effects and random error for $N = 250$ hypothetical treatment and control patients based on the appropriate covariance structures (e.g., \mathbf{G}). Then simulated OCT response values were computed based on the fixed and random effects and random error of Equation (4). For each replication, the null hypothesis of $H_0: \delta = 0$ was evaluated with the Z-test based on a LMM fit to the simulated data. The process was repeated 1000 times for each effect size value of δ and the average number of rejections of H_0 was taken to be the estimated power. Results of the simulation are shown in the table below.

Table 9.2. Power as a Function of Effect Size based on the OCT Simulation Study

Effect Size	Power
30%	0.515
35%	0.603
40%	0.665
45%	0.782
50%	0.855

As the table shows, the power surpassed the conventional cutoff of 0.80 only for the largest effect size, but the next lower size (45%) was close to the cutoff. The results indicate that $N = 250$ might provide adequate power for the treatment and placebo slope comparison of OCT if the effect size is large, but power might be lower than the conventional cutoff for medium and smaller effect sizes.

9.6. Major Secondary Objective (d): *Evaluate the activity of Ibudilast (MN-166) versus placebo as measured by cortical atrophy, as measured by cortical longitudinal atrophy detection algorithm.*

No pilot data or other effect size estimates were available for CLADA. However, we expect CLADA effects to be consistent with those of the other secondary endpoints. Therefore, we are confident that statistical power for CLADA will be sufficient to detect effect sizes similar to those discussed for the other secondary endpoints.

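### The MTR power table counts all 125 patients per arm and allows for no dropout; with the plan's own 10% dropout, its stated method puts both t.i.d. rows below 0.80

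*Combined protocol and SAP*

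**What the plan says.** For the primary endpoint, SAP 9.1 states: "A 10% dropout rate was assumed and all estimated sample sizes were inflated by this percentage". The inflation is by a factor of 1.10, and 125 per arm is the number after it. Protocol 12.1.3 says the same.

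For MTR, SAP 9.4 and protocol 12.1.3 had no pilot data and borrowed summary results from a trial of BG-12 in relapsing MS: "The statistics available for the study were means of change scores and their standard deviations". Power was therefore computed for an independent t-test of the change from baseline to two years, with the square root of 125 in the formula. Table 9.1 gives 0.856 (b.i.d., all patients), 0.803 (t.i.d., all), 0.925 (b.i.d., no lesions) and 0.816 (t.i.d., no lesions). Here b.i.d. and t.i.d. are the two BG-12 regimens of the source trial.

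Two sentences interpret the table against 0.80. The first says that "the lowest estimated power (t.i.d., all patients) was greater than the conventional cut-off of 0.80". The second says that in patients without new lesions, whom the plan regards as closer to this trial's population, power is higher still. On the significance level, SAP section 6 says that "all analyses to address the primary and major secondary objectives will be conducted at the 0.10 significance level".

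**The concern.** The same 125 is used in two senses. For BPF it is the number randomised, before losses. For MTR it is the number with a two-year measurement. Both endpoints come from the same patients and the same MRI visits, and SAP 7.1 says that missing data through dropout are expected. In a two-point change-score test, a patient without a two-year scan contributes nothing, so the dropout allowance belongs in the MTR calculation as well.

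The lowest figure, 0.803, clears 0.80 by only 0.003, so even a small loss changes what the text can say. At stake is how a null MTR result would be read: the reader would set it against a stated chance of detection that the calculation does not support. SAP 9.6 also rests its confidence in CLADA power on the other secondary endpoints.

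**Working it through.** **Inputs.** Significance level 0.10 (SAP section 6), two-sided as in the SAP 9.4 formula, so the critical value is 1.6449. Number per arm 125 (SAP 9.4). Dropout 10%, applied as a factor of 1.10 (SAP 9.1). The four powers of Table 9.1. The mean difference δ and the SD σ are not printed.

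**Formula (SAP 9.4).** Power = Φ(|δ|√n/σ − 1.6449).

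**The plan's own figure.** Without δ and σ, 0.803 cannot be reproduced independently. The ratio can only be solved back from it: |δ|√125/σ = 1.6449 + z(0.803) = 1.6449 + 0.8524 = 2.4972, so |δ|/σ = 0.2234. Putting this back returns 0.803, which is circular and confirms only that the formula is being read as written.

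**Number completing.** By the plan's convention, 125/1.10 = 113.6 per arm. Read instead as 10% of 125 lost, it is 0.90 × 125 = 112.5.

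**Restated power.** At 113.6 per arm the term |δ|√n/σ is divided by √1.10 = 1.0488. For t.i.d., all patients: 2.4972/1.0488 = 2.3810; 2.3810 − 1.6449 = 0.7361; Φ(0.7361) = 0.769.

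| Row of Table 9.1 | Stated, n = 125 | Term at 125 | Term at 113.6 | Power at 113.6 | Power at 112.5 |
|---|---|---|---|---|---|
| b.i.d., all | 0.856 | 2.7074 | 2.5814 | 0.825 | 0.822 |
| t.i.d., all | 0.803 | 2.4972 | 2.3810 | 0.769 | 0.766 |
| b.i.d., no lesions | 0.925 | 3.0844 | 2.9408 | 0.903 | 0.900 |
| t.i.d., no lesions | 0.816 | 2.5451 | 2.4266 | 0.783 | 0.779 |

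**Sensitivity.** The t.i.d., all-patients row needs 123.9 per arm for 0.80; at 123 it is 0.797. If the table had been built with two-sided 0.05 or one-sided 0.10, the same row would fall to between 0.760 and 0.774 over the two dropout conventions. The conclusion does not depend on the significance level or on sidedness.

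**Planned analysis, as an illustration.** The t-test stands in for a mixed model with up to five visits. To see what that model might give for the t.i.d., all-patients case, I assumed: a linear effect; independent residuals; a common intercept as in SAP 7.1 (SAP 8.2 models change from baseline with baseline as covariate, so this is an approximation); intercept variance 5 or 50 times the residual variance; and 10% dropout, 2.5% after each of the first four visits. The two-point change then has variance equal to the slope variance over 96 weeks plus twice the residual variance, and its standardised effect is fixed by 0.803 at 125 per arm.

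| Slope variance / residual variance | Power (intercept ratio 5) | Power (intercept ratio 50) |
|---|---|---|
| 0.5 | 0.852 | 0.836 |
| 1 | 0.840 | 0.827 |
| 2 | 0.825 | 0.815 |
| 5 | 0.807 | 0.802 |
| 10 | 0.799 | 0.796 |
| 20 | 0.795 | 0.793 |

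The documents give no value for these ratios, so they do not settle on which side of 0.80 the planned model falls.

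**The case against.** The strongest reply is that the two-point t-test is not the planned analysis. SAP 8.2 specifies a mixed model across visits, which keeps incomplete cases. Patients who stop study drug are still asked to have scans every 24 weeks, and the mITT population needs only one assessment after baseline. Charging for dropout without crediting the intermediate scans is one-sided. This stands. A reader might infer that the design delivers only 0.77 for MTR; the documents do not support that, and the illustration above runs from about 0.79 to 0.85. It does not rescue the printed figures, which come from the t-test.

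A reader might also call the quoted sentence false. It is not: 0.803 exceeds 0.80 at 125 per arm, and the SAP says only that the sample size might be sufficient. The fault is an omitted allowance, not a miscalculation.

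A reader might extend the point to OCT. SAP 9.5 says that random effects and errors were generated for 250 "hypothetical treatment and control patients based on the appropriate covariance structures" but does not state the visits or the dropout used. That no dropout was simulated would be a guess. Even on that guess the OCT conclusion is unchanged: only the 50% effect exceeds 0.80.

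Nor is the earlier ibudilast trial a basis for a heavier loss. "Two-year completion of the 60 mg/d group was 86"% describes completion in one arm of a relapsing-MS trial that included an extension period. It is not this plan's assumption about available scans. Finally, the whole-brain source of the MTR data is not undisclosed; SAP 9.4 states it.

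**Conclusion.** The point holds for MTR, as an inconsistency between SAP 9.1 and SAP 9.4 (and within protocol 12.1.3). By the stated method with the plan's own 10% dropout, the powers are about 0.77 to 0.90 rather than 0.80 to 0.93, a drop of about 0.02 to 0.03 in each row. Both t.i.d. rows fall below 0.80 and both b.i.d. rows stay above it. The claim about the lowest power is therefore not supported, and the claim about patients without new lesions is not supported for t.i.d.

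This rests on two assumptions: that the 10% given for the primary endpoint applies to MTR, which is reasonable because the patients and scan visits are the same, and that patients who drop out contribute nothing, which is true of the t-test but not of the planned model. The effect on the trial is small. The primary endpoint fixes the sample size, and no test or decision rule changes.

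**What to change.** Choose one of two routes for SAP Table 9.1 and the matching table in protocol 12.1.3.

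1. Restate the four powers at 113.6 per arm (about 0.825, 0.769, 0.903 and 0.783) and label them as completers-only figures from the two-point t-test.
2. Replace them with a simulation of the planned MTR mixed model with 10% dropout, stating the variance components assumed. This may bring power to near or above 0.80.

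In either case, revise the sentence on the lowest power and the sentence on patients without new lesions to match, in both documents. For OCT, add one line to SAP 9.5 giving the visits and dropout used in the simulation; no figures there need restating on present evidence.

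The first route is a text change and the second a short simulation. Neither needs more patients or alters the analysis. The cost is a slightly less favourable power statement under the first route.

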10. SAFETY MONITORING

10.1. Assessment & Recording of Adverse Events

The clinical study site PI (CSSPI) or an authorized physician will assess all AEs for severity, relationship with study medication, and whether it meets the criteria for classification as an SAE, requiring immediate notification to the Sponsor or designee. These assessments will be made in accordance with the standard ratings detailed in the following sections. Each CSSPI and research team is responsible for identifying adverse events and reporting them through the DCC Online Adverse Event Reporting System (AERS).

Adverse events should be collected and recorded for each subject from the date the informed consent form was signed until the end of their participation in the study (i.e., the subject has discontinued or completed the study) through the follow-up visit with the exception of those who discontinue study medication during the study and are followed on a semi-annual basis. Subjects who discontinue study medication but continue follow-up within the study will not have AEs collected after study drug discontinuation. Only those AEs that occurred while on study drug that have not been resolved will be followed until resolution or stabilization.

Adverse events may be volunteered spontaneously by the study subject, or discovered by the study staff during physical examinations, or by asking an open, non-leading question such as, "How have you been feeling since you were last asked?" All AEs and any required remedial action will be recorded in the subject's source documentation and transcribed onto the appropriate CRF page for the study period indicated. The nature of AE, date (and time, if known) of AE onset, date (and time, if known) of AE outcome to date, severity, and action taken of the AE will be documented together with the CSSPIs or an authorized physician's assessment of the seriousness of the AE and causal relationship to study medication and/or study procedure (at the time of assessment).

All AEs should be recorded individually in the study subject's own words (verbatim) unless, in the opinion of the PI or an authorized physician, the AEs constitute components of a recognized condition, disease, or syndrome. In the latter case, the condition, disease, or syndrome should be named rather than each individual symptom. The AEs will subsequently be coded using the MedDRA.

Appropriate measures should be taken to treat AEs as necessary, and the response of the study subject should be monitored and recorded. Clinical, laboratory, and diagnostic measures should be obtained as needed, and the results of which should be recorded in the subject's source documentation and transcribed onto the appropriate CRF page.

The CSSPI or an authorized delegate is responsible for submitting the requested information via the DCC Online Adverse Event Reporting System within 24 hours or as soon as possible after learning of the event. Following the end of the subject's participation in the study, the CSSPI or an authorized delegate should report SAEs "spontaneously" if considered at least possibly related to study medication. Upon entry of a serious adverse event by a CSSPI, the DCC Online Adverse Event

Reporting System will immediately notify the Medical Safety Monitor (MSM).

10.2. Severity Assessment

The severity of AEs will be determined as described below:

- Mild (Grade 1): Ordinarily transient symptoms that do not influence performance of subject's daily activities. Treatment is not ordinarily indicated.
- Moderate (Grade 2): Marked symptoms sufficient to make the subject uncomfortable. Moderate influence on performance of subject's daily activities. Treatment may be necessary.
- Severe (Grade 3): Symptoms cause considerable discomfort. Substantial influence on subject's daily activities. May be unable to continue in the study and treatment may be necessary.
- Life-Threatening (Grade 4): Extreme limitation in activity, significant assistance required; significant and urgent medical/therapy intervention required. Hospitalization probable.
- Death (Grade 5): Death related to AE.

When changes in the intensity of an AE occur more frequently than once a day, the maximum intensity for the event should be noted for that day. Any change in grade of severity of signs and symptoms over a number of days will be captured by recording a new AE, with the amended severity grade and the date (and time, if known) of the change.

10.3. Medical Safety Monitor

As previously indicated, [name] will serve as the MSM for this trial. In addition to performing real-time reviews of all SAEs (as described in [section 2.2](#)), [name] will also receive quarterly tabulations, by blinded treatment group, of all AEs/SAEs for the purpose of determining if any safety trends exist that may raise concerns. Safety will be assessed in two ways – both the percentage of subjects who experience any AE and the rate of AEs will be compared by body system across the two groups. The additional questions related to whether the AE/SAE is related to treatment and/or whether the AE/SAE is unanticipated will be used to subset these into a series of additional tables. This quarterly review will identify any disconcerting discrepancy in the frequency of any AE/SAE between the two groups.

11. INTERIM ANALYSES

11.1. Interim Safety Monitoring

After 30 patients have been enrolled for at least 30 days and 60 patients have been enrolled for at least 60 days, the Medical Safety Monitor will review pooled (i.e., blinded to treatment) safety data provided by the DCC. Beginning after approximately month 3 of enrollment start, a National Institute of Neurological Disorders and Stroke (NINDS) Data and Safety Monitoring Board (DSMB) will meet every six months during the study (and more often, if deemed necessary), and will review blinded safety data including adverse events and serious adverse events (SAE). The DSMB will be empowered to recommend stopping the study at any time due to safety concerns.

